**Table 2: Schedule of Events**

Study Period	Screening	Baseline	Treatment				6 Weeks Post D/C
Study Week (±7 Days)	Day 1 a	Day 1 a	Every 12 Weeks	Every 24 Weeks	Every 48 Weeks b	End of TX	
Informed consent c	X	X					
Clinical history d	X	X					
Vital signs	X				X	X	X
Height	X						
Weight	X	X		X e	X	X	X
Physical examination	X						
Hepatitis B and C f	X						
Hematology	X				X	X	X
Biochemistry	X				X	X	X
Drug dispensed		X	X g	X g	X g		
Pre-/post-shipment communication			X h	X h	X h		
Drug compliance			X i	X i	X i	X	
Adverse events	X	X	X i	X i	X i	X	X
Concomitant medication	X	X	X i	X i	X i	X	X

**Abbreviations:** D/C, discontinuation; TX, treatment

a Subjects who have not participated in an ataluren study in the past year are required to complete all assessments identified under screening. Subjects who have participated in an ataluren study within the past year only need to complete the assessments identified under baseline.

b Annual visits will occur every 48 weeks (ie, Weeks 48, 96, 144, 192, 240, 288, 336, 384, 432, 480, 528, 576, 624, 672, 720, etc).

c Informed consent will be signed before any study procedures are performed.

d Clinical history will be collected for ataluren-naïve subjects (siblings). For subjects enrolling from another ataluren clinical study, only clinical history reported since the last dose of ataluren in the prior DBMD study will be collected.

e Reminders will be communicated prior to every 24 week visit for subject to obtain a weight check-in between the annual visits at sites. This communication will be documented in the source.

f Hepatitis B and C testing is only required for ataluren-naïve subjects (siblings) or subjects who have a temporary treatment gap of 1 year before entering Study 016.

g Drug will be dispensed to the subject every 12 weeks.

h Clinical site staff will contact the subject or parent(s)/legal guardian(s) to confirm details and timing of the upcoming study drug shipment. Post-shipment contact will confirm receipt of and condition of study drug.

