i Subjects or parent(s)/caregiver(s) or legal guardian(s) should return all used and unused cartons and unused sachets of ataluren as instructed in order to assess study drug compliance.

j Clinical site staff will contact subject or parent(s)/legal guardian(s) every 12 weeks (by phone, email, or text if there is no clinic visit) to assess adverse events and concomitant medications.

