**Table 3: Schedule of Events for PTC124-GD-048-DMD Subjects**

Study Period Study Week (±7 Days)	Scr/Baseline Day 1 a	Treatment						6 Weeks Post D/C
		Week 14 b	Week 28 b	Week 40 Through End of TX				
				Every 12 Weeks c	Every 24 Weeks c	Every 48 Weeks c	End of TX	
Informed consent d	X							
Clinical history e	X							
Vital signs	X		X			X	X	X
Height	X	X	X					
Weight	X	X	X		X f	X	X	X
Physical examination	X							
Hepatitis B and C g	X							
Hematology		X	X			X	X	X
Biochemistry		X	X			X	X	X
Drug dispensed	X	X h	X h	X i	X i	X i		
Pre-/post-shipment communication		X		X i	X i	X i		
Drug compliance	X	X	X	X k	X k	X k	X	
Adverse events	X	X	X	X l	X l	X l	X	X
Concomitant medication	X	X	X	X l	X l	X l	X	X
PDMS-2	X	X	X					

**Abbreviations:** D/C, discontinuation; PDMS-2, [Peabody Developmental Motor Scale](#), second edition; Scr, screening; TX, treatment

a Screening/baseline (Day 1) of the current study may be the same day as visit 5 (Week 24) in Study [PTC124-GD-048-DMD](#), in which case, corresponding assessments in the two studies do not need to be repeated.

b Weeks 14 and 28 of the current study represent 38 and 52 weeks, respectively, of ataluren treatment for these Study 048 subjects.

c After the Week 28 visit, assessments will be conducted as outlined in the table every 12 weeks, every 24 weeks, and every 48 weeks. These visits will be anchored by the visit date for Week 28. The visit following Week 28 should be the first every 12 week visit at approximately Week 40 post-enrollment. Annual visits will occur every 48 weeks (ie, Weeks 76, 124, 172, etc).

d Informed consent will be signed before any study procedures are performed.

e Clinical history reported since the last dose of ataluren in Study 048 will be collected.

f Reminders will be communicated prior to every 24 week visit for subject to obtain a weight check-in between the annual visits at sites. This communication will be documented in the source.

g Hepatitis B and C testing is only required for ataluren-naïve subjects (siblings) or subjects who have a temporary treatment gap of 1 year before entering Study 016.

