#### **7.2.1.2. Treatment Visits during Study**

Study visits will occur every 12 weeks, 24 weeks, and 48 weeks during the treatment period. The subject is required to complete a visit at the clinical research facility every 48 weeks. Every 24 weeks, the subject is required to have a weight check. A study drug shipment will be sent to the subject/caregiver's home every 12 weeks. Clinical site staff will contact the subject (pre-and post-study drug dispensing) to notify of upcoming study drug shipment and to confirm study drug receipt. Phone conversations will be conducted to monitor and capture AEs and use of concomitant medications.

Subjects previously enrolled in [PTC124-GD-048-DMD](#) will complete 2 additional visits as indicated in [Table 3](#). Subjects will report to the clinical research facility for a Week 14 and Week 28 visit. After the Week 28 visit, study visits will follow the 12 weeks, 24 weeks, and 48 weeks schedule.

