## 8. ADVERSE EVENT ASSESSMENTS

### 8.1. Adverse Event Definitions

#### 8.1.1. Adverse Events

An AE is any untoward medical occurrence associated with the use of a drug (investigational medicinal product) in humans, whether or not it is considered related to the drug. An AE can therefore be any unfavorable and unintended sign (including an abnormal laboratory finding), symptom, or disease in a study subject who is administered ataluren in this study.

For this protocol, untoward medical occurrences that should be reported as AEs include the following:

- All AEs during the course of treatment with ataluren.
- All AEs resulting from medication misuse, abuse, withdrawal or overdose of ataluren.
- All AEs resulting from medication errors such as dispensing or administration error outside of what is described in the protocol.
- Worsening of a preexisting illness.
- Injury or accidents. Note that if a medical condition is known to have caused the injury or accident (a fall secondary to dizziness), the medical condition (dizziness) and the accident (fall) should be reported as 2 separate AEs.
- Abnormalities in physiological testing or physical examination findings that require clinical intervention or further investigation (beyond ordering a repeat [confirmatory] test).
- Laboratory or ECG abnormalities that require clinical intervention or further investigation (beyond ordering a repeat [confirmatory] test) unless they are associated with an already reported clinical event. Laboratory abnormalities associated with a clinical event (e.g., elevated liver enzymes in a subject with jaundice) should be captured in the source documents. Laboratory abnormalities not requiring clinical intervention or further investigation will be captured as part of overall laboratory monitoring and should not be reported as AEs.

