#### **10.4.5. Primary Variables**

##### ***10.4.5.1. Adverse Events***

Adverse events will be classified using the MedDRA classification system. The severity of AEs will be graded according to the CTCAE, Version 5.0 whenever possible. A treatment-emergent adverse event is defined as an AE that occurs or worsens in the period extending from a subject's first ataluren dose in this study to 6 weeks after the last ataluren dose in this study.

The frequency of subjects experiencing a specific AE will be tabulated by visit, body system, and MedDRA term. In the by-subject analysis, a subject having the same event more than once will be counted only once using the worst CTCAE grade.

Adverse events classified as CTCAE Grade 3 or higher; study-drug-related events; adrenal, hepatic, and renal events leading to special diagnostic evaluations; events leading to discontinuation from treatment; and SAEs will be considered with special attention.

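### By-visit AE tables will show the 48-weekly testing calendar, not the timing of risk, for asymptomatic AEs found by laboratory tests or vital signs

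*Protocol*

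**What the plan says.** **Time unit.** Section 10.4.5.1, repeated in the synopsis under Statistical Methods, states: "The frequency of subjects experiencing a specific AE will be tabulated by visit, body system, and MedDRA term".

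**AE collection.** A footnote to Table 2 reads "Clinical site staff will contact subject or parent(s)/legal guardian(s) every 12 weeks (by phone, email, or text if there is no clinic visit"). Table 3 has the same footnote for the visits after Week 28. The AE row is marked in every 12-, 24- and 48-week column.

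**Testing.** Section 7.2.1.2 says "The subject is required to complete a visit at the clinical research facility every 48 weeks". In Table 2, hematology, biochemistry and vital signs are marked at screening, every 48 weeks, End of Treatment and 6 weeks after discontinuation. The 12- and 24-week columns are blank for all three. Table 3 gives Study 048 subjects laboratory tests at Weeks 14 and 28 and vital signs at baseline and Week 28. It then uses the same 48-week spacing (Weeks 76, 124, 172).

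**What becomes an AE.** Section 8.1.1 counts "Laboratory or ECG abnormalities that require clinical intervention or further investigation (beyond ordering a repeat [confirmatory] test"), unless they belong to a clinical event already reported. Physiological-test findings have a parallel rule.

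**Timing.** Section 2 names timing among the features that are to characterise the safety profile.

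**The concern.** An AE table has no blank cell for a visit without a test. A silent rise in creatinine, a low blood count, a raised lipid value or a raised blood pressure has little chance of being seen at a phone, email or text contact. The by-visit table shows that contact as few or no events, which reads as absence of risk. The abnormalities that built up over the preceding 48 weeks then appear together at the annual visit.

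The End-of-Treatment and 6-week post-discontinuation visits also carry tests, so events gather there too and could be mistaken for an effect of stopping the drug. Both patterns would arise with constant risk and complete follow-up. Renal findings are among those affected, and Section 10.4.5.1 gives special attention to renal events that lead to diagnostic evaluation.

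**Working it through.** The protocol gives no figure for this point, so there is nothing to reproduce. The check has two parts.

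**1. Share of contacts with scheduled tests**

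- Table 2: the listed annual weeks are the multiples of 48 up to 720. That is 720/48 = 15 annual visits among 720/12 = 60 contacts, or 25%.
- Over the stated duration of about 13 years: 13 × 365.25/7 ≈ 678 weeks, giving 14 annual visits among 56 contacts, again 25%.
- Table 3 after Week 28: "These visits will be anchored by the visit date for Week 28", and (76 − 28)/12 = 4. Weeks 40, 52 and 64 have no tests and Week 76 does.
- Table 3 in full to Week 720: laboratory tests fall at 16 of 59 post-baseline visits (27%) and vital signs at 15 of 59 (25%).

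**2. Illustration under constant risk**

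N = 270 is the planned enrolment. The other inputs are assumptions:

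- h: share of subjects with a new test-detectable AE per 12 weeks.
- u: share of these found off-schedule within their own 12-week window.
- p: probability per 12 weeks that an unfound abnormality persists to the annual test.

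Expected count at a non-annual visit = N·h·u.

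Expected count at an annual visit = N·h·[u + (1 − u)(1 + p + p² + p³)].

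The ratio of annual to non-annual is [u + (1 − u)(1 + p + p² + p³)]/u, in which h cancels. For example, with u = 0.5 and p = 0.5 it is [0.5 + 0.5 × 1.875]/0.5 = 2.9.

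| Found off-schedule (u) | p = 1 | p = 0.5 | p = 0 |
|---|---|---|---|
| 0 | all at tested visits | all at tested visits | all at tested visits |
| 0.25 | 13.0 | 6.6 | 4.0 |
| 0.50 | 5.0 | 2.9 | 2.0 |
| 0.75 | 2.3 | 1.6 | 1.3 |

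Expected counts with h = 1% (N·h = 2.7):

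- u = 0, p = 1: 0 at each of three visits, then 2.7 × 4 = 10.8 at the fourth.
- u = 0.5, p = 1: 1.4, then 6.8.
- u = 0.5, p = 0: 1.4, then 2.7.

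With h = 0.5% or 2% the counts halve or double and the ratios stay the same.

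**The case against.** - **Details may sit in the SAP.** The protocol does not say how an AE is assigned to a visit or which columns are shown, and by-visit tabulation does match how AEs are collected. This stands in part. But the protocol itself fixes the visit as the unit, in two places, and following it as written produces the pattern.
- **The affected set is narrow.** This stands. Section 8.1.1 excludes abnormalities that need no action and those tied to a reported clinical event. Symptomatic AEs are asked about every 12 weeks.
- **Tests also happen off-schedule.** This stands too. A reader might infer that test-detected AEs can surface only at every fourth visit, but the protocol does not support that. Section 6.4.1 calls for creatinine and BUN before and repeatedly during IV aminoglycoside or vancomycin therapy. The footnote to Table 1 allows immediate confirmation of renal values. Section 6.3.2 provides for further work-up, and routine care may add more. The row with u = 0 is therefore a limit, not an expectation.
- **Timing is visible elsewhere.** Laboratory and vital-sign summaries by visit hold data only where tests were done, and onset dates are recorded (Section 8.3). This softens the harm. It does not correct the AE table, and the onset of a silent abnormality before its first abnormal test is not known.
- **Nothing is tested.** The study is open-label and descriptive, and no decision rule uses this table. That limits the consequence to misreading.

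**Conclusion.** The point holds for asymptomatic AEs found by scheduled tests. Their by-visit pattern will peak at annual and exit visits under constant risk. The size cannot be known from the protocol, which gives no incidence, persistence or off-schedule detection. Under the assumptions shown, the annual visit carries about 1.3 to 2.3 times the count of another visit when three quarters are found off-schedule, and 2 to 5 times when half are. With none found off-schedule, all fall at tested visits.

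A reader might go further and infer that all by-visit AE tables are unsound, or that AE incidence is understated. The documents do not support either. AEs reported at the 12-weekly contacts are unaffected. The number of subjects with an AE changes only through transient abnormalities that come and go between tests. The distortion is in timing.

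**What to change.** In Section 10.4.5.1 and the synopsis, add a summary of AEs by onset in consecutive 48-week periods, each ending at and including the annual visit. For Study 048 subjects, use Day 1 to Week 28 as one period (it holds two laboratory assessments), then periods ending at Weeks 76, 124 and so on.

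Make this the timing table for investigation-type, renal, hematological, lipid and blood-pressure terms. Select them by MedDRA term: the AE items in Section 8.3 include no mode of detection, and selection by term needs no new field.

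By-visit tabulation may stay for the other AEs. Add a footnote stating which visits carry scheduled tests, including the End-of-Treatment and 6-week post-discontinuation visits. A subject's last period can contain both exit tests, so the same footnote belongs on the 48-week table.

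Cost: wording in two places, one additional table, and coarser time resolution for the selected terms. The data are already collected. The delay between true onset and detection remains. For a persistent abnormality found only at the annual test it can reach 48 weeks, and averages 48/2 = 24 weeks if onset is uniform over the interval. That delay comes from the testing schedule, and re-tabulation does not shorten it.

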##### ***10.4.5.2. Laboratory Data***

Hematological, serum biochemistry, adrenal laboratories, and urine data and their changes (only for continuous laboratory parameters) from baseline will be summarized by visit. Hematological, serum biochemistry, adrenal laboratories, and urine data will be graded according to CTCAE severity grade when applicable. For parameters for which a CTCAE scale does not exist, the frequency of subjects with values below, within, and above the normal ranges will be summarized. Summary tables will be presented for each relevant assay to show the number of subjects by severity grade with corresponding percentages. Subjects will be characterized only once for a given assay, based on their worst severity grade observed during the time period of interest.

Shift tables for hematology, serum biochemistry, adrenal laboratories, and urine data will also be presented showing change in CTCAE severity grade from baseline to each visit. For parameters for which a CTCAE scale does not exist, shift tables will be presented showing change in results from baseline (normal, low and high [or abnormal]) to each visit (normal, low and high [or abnormal]).

Separate listings and tables will be created for parameters for assessment of adrenal, hepatic, and renal monitoring based on the conditions listed in Section 6.3.

**10.4.5.3. *Physical Findings***

Physical findings (weight, physical examination data, systolic and diastolic blood pressure, radial pulse rate, and body temperature) will be listed and summarized by visit. Where appropriate, changes from baseline at each visit will be summarized and tested using the paired t-test or a nonparametric alternative.

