Corticosteroids, working through unknown mechanisms, have been the only medications to demonstrate a benefit in ameliorating the manifestations of DBMD (Mendell 1989, Griggs 1991, Fenichel 1991a, Fenichel 1991b, Biggar 2001, Beenakker 2005a, Biggar 2006, Pradhan 2006). Clinical improvement, primarily measured by muscle strength testing and timed function tests (standing from supine, climbing stairs, and running 10 meters), is seen within ~2 months after starting treatment and disease progression appears to be slowed (Beenakker 2005a, Biggar 2006, Pradhan 2006). In addition, corticosteroid usage appears to slow the rate of forced vital capacity (FVC) decline, substantially reducing decreases in any 6- to 12-month period (Mendell 1989, Griggs 1991, Biggar 2001, Biggar 2006). Most boys receiving corticosteroids experience physically and socially distressing growth inhibition, interruption of pubertal changes, and disfiguring Cushingoid facies and habitus (Manzur 2008). Many boys have weight gain (which is problematic given the need to reduce muscle load-bearing). Behavioral problems, osteopenia with a high rate of fractures (Biggar 2006), gastric ulceration, rashes, glucose intolerance, and cataracts are also observed. Because chronic corticosteroid use in children with DBMD is

typically associated with serious sequelae, corticosteroids are not universally employed. No treatment is currently available to address the underlying cause of the disease by restoring the missing dystrophin in muscle.

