### **3. STUDY DESIGN**

This study comprises an open-label, safety study of ataluren in subjects who previously received ataluren at an investigational site in a prior PTC-sponsored clinical study or treatment plan and siblings of those subjects. Only subjects enrolling in the current study from [PTC124-GD-048-DMD](#) (Study 048) will have efficacy assessments (ie, [Peabody Developmental Motor Scale](#), second edition [PDMS-2]) performed for up to 52 weeks from the date of first dosing in Study 048.

This study will be performed at investigational sites in the US and Canada. It is planned that approximately 270 subjects will be enrolled. Subjects will receive ataluren 3 times per day (TID) at respective morning, midday, and evening doses of 10 mg/kg, 10 mg/kg, and 20 mg/kg. Study assessments will be performed during screening, on the first day of ataluren dosing, and then every 12, 24, and 48 weeks as described in [Table 2](#).

For subjects from Study 048 only, study assessments will be performed and motor development will be assessed using the PDMS-2 at baseline/Day 1, Week 14, and Week 28. After the Week 28 visit, study assessments will be performed every 12, 24, and 48 weeks as described in [Table 3](#).

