## **5. ENROLLMENT PROCEDURES**

### **5.1. Source and Number of Subjects**

Subjects with nmDBMD who received ataluren treatment in a prior PTC-sponsored clinical trial or treatment plan at a study site and siblings of those subjects are all potential candidates for this study. Approximately 270 subjects will be enrolled.

It is anticipated that subjects will be enrolled from investigator sites in the US and Canada.

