## **10. STATISTICS AND DATA MANAGEMENT**

### **10.1. Sample Size Calculation for the Primary Endpoint**

The sample size for this study is based on the number of subjects in previous ataluren DBMD studies and is not based upon any formal statistical hypothesis.

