### **10.3. General Statistical Considerations**

By-subject listings will be created for each CRF module.

Summary tables for continuous variables, overall and by corticosteroid use, will contain the following statistics: n, mean, standard deviation, standard error, 95% confidence intervals on the mean, median, minimum, and maximum. In addition, changes from baseline will be likewise summarized. If continuous data have substantial non-normality, log-transformed data or nonparametric tests may be employed, as appropriate.

Summary tables for categorical variables, overall and by corticosteroid use, will include N, n, and percentages.

Unless otherwise specified, all analyses will be 2-sided at the 0.05 level of significance.

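### Testing raw weight change from baseline against zero in growing boys with no control arm gives near-certain significance that says nothing about ataluren

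*Protocol*

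**What the plan says.** Section 10.4.5.3 of the protocol, repeated in the synopsis under Statistical Methods, covers these variables: "Physical findings (weight, physical examination data, systolic and diastolic blood pressure, radial pulse rate, and body temperature) will be listed and summarized by visit". It continues that, where appropriate, "changes from baseline at each visit will be summarized and tested using the paired t-test or a nonparametric alternative". No criterion is given for when testing is appropriate, and no age-standardised score, percentile or normative reference is named.

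Section 10.3 fixes the level: "Unless otherwise specified, all analyses will be 2-sided at the 0.05 level of significance". It also plans means, standard deviations and 95% confidence intervals for continuous variables and their changes from baseline, overall and by corticosteroid use.

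On design, section 3 states: "This study comprises an open-label, safety study of ataluren in subjects who previously received ataluren", together with siblings of those subjects. The synopsis lists reference therapy as not applicable and gives a duration of about 13 years. On size, section 5.1 states: "Approximately 270 subjects will be enrolled". Section 10.1 says that the sample size "is not based upon any formal statistical hypothesis".

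Section 1.1 puts first manifestation of the disease at about 3 to 7 years of age and describes growth inhibition under corticosteroids. On weight it adds: "Many boys have weight gain (which is problematic given the need to reduce muscle load-bearing".

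**The concern.** A paired test against zero answers one question: has the mean changed since baseline? In a cohort made up mainly of growing boys, the answer for weight is yes before any data are seen. The protocol itself names a second cause of weight change, corticosteroids. With no concurrent control, a rejection cannot be assigned to ataluren, to growth or to steroids.

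The direction of the result matters too. For a drug given to children, one of the weight signals worth detecting is gain that is too slow. Raw weight would still rise in that case, so the test would return the same result as in healthy growth: a significant increase. The study's stated objective is safety and tolerability, and this test adds a p-value to the safety output without separating the cases that a safety reader needs separated.

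Blood pressure and pulse also change with age, so the same confounding builds up over years of follow-up, though more slowly.

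**Working it through.** The protocol states no power or growth calculation, so there is no figure of its own to reproduce. The check is how often the planned test rejects from growth alone.

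**Inputs from the protocol:** paired t-test, two-sided 0.05; about 270 subjects planned; Table 2 schedules weight every 24 weeks and vital signs every 48 weeks.

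**Assumptions (not in the protocol):** mean change, SD of change, and number of subjects with data at a visit. Ranges are shown because the results depend on them.

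**Formula:** with mean change d, SD of change s and n subjects, the noncentrality is d/s × √n. The rejection probability is the chance that a noncentral t with n − 1 degrees of freedom lies beyond the two-sided 5% critical value.

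**Weight at 48 weeks, gain 2 to 4 kg, SD 3 to 5 kg**
- Least favourable case (2 kg, SD 5), n = 100: 2/5 × 10 = 4.00, critical value 1.984, probability 0.977.
- Same case, n = 50: 2/5 × 7.07 = 2.83, critical value 2.010, probability 0.792.
- Same case, n = 30: probability 0.56.
- All other combinations in the range are higher, up to about 1.00.
- Central illustration (2.5 kg, SD 3): n = 20 gives 2.5/3 × 4.47 = 3.73 and probability 0.942; n = 50 gives 5.89 and probability 0.9999.

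**Weight at 24 weeks, gain 1 to 2 kg, SD 2 to 4 kg:** 0.98 or more at n = 270, 0.70 to about 1.00 at n = 100, and 0.41 to about 1.00 at n = 50.

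**Halved gain, 1.25 kg per 48 weeks, SD 3 kg**
- n = 50: 1.25/3 × 7.07 = 2.95, probability 0.82.
- n = 100: 1.25/3 × 10 = 4.17, probability 0.98.

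These rejections are in the direction of gain. At n = 100 the 95% interval has half-width 1.984 × 3/10 = 0.60 kg. A gain of 2.5 kg then has an interval of about 1.90 to 3.10 kg, and a gain of 1.25 kg about 0.65 to 1.85 kg. Both exclude zero, so the p-value reads the same. The estimates differ clearly, but only to a reader who knows what gain to expect at those ages.

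**Blood pressure and pulse**

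| Assumed drift | n = 100 | n = 270 |
|---|---|---|
| Systolic 0.5 to 2 mmHg at 48 weeks, SD 8 to 12 | 0.07 to 0.70 | 0.10 to 0.98 |
| Pulse 0.5 to 2 bpm at 48 weeks, SD 10 to 14 | 0.06 to 0.51 | 0.09 to 0.91 |
| 2.5 units at 240 weeks, SD 10 to 14 | 0.42 to 0.70 | 0.83 to 0.98 |
| 5 units at 240 weeks, SD 10 to 14 | 0.94 or more | about 1.00 |

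For example, a 1 mmHg drift with SD 10 at n = 100 rejects with probability 0.17. Near-certainty therefore applies to weight, and to blood pressure and pulse only after several years of drift with enough subjects remaining.

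The nonparametric alternative does not change the picture, because it also tests for no shift from baseline.

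**The case against.** The strongest reply is that the protocol tests only where appropriate, so an analysis plan could exclude weight or put it on another scale, and derivations of standardised scores usually belong there. It stands to this extent: a reader might infer that every variable must be tested at every visit, and the text does not require that. It does not remove the point. The protocol itself names the test, the contrast and the level, lists weight first among the variables, and gives no criterion that would exclude it.

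Second, the other planned output limits the harm. Section 10.3 already provides means and confidence intervals for change, section 10.4.5.3 provides listings, and section 8.1.1 makes examination abnormalities that need intervention or further investigation reportable as adverse events. A reader might infer that poor weight gain would go unseen. The documents do not support that; the test fails to show it, but other output could. Section 10.3 also asks only for summaries by corticosteroid use, so it should not be read as calling for separate tests in those subgroups.

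Third, no trial decision rests on these tests, since there is no formal hypothesis. That is correct, and it limits the consequence to misleading p-values in the safety report.

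Fourth, standardised scores are not a clean remedy. Corticosteroids and disease progression can move a boy away from a general-population reference without any drug effect, and sexually active fertile men are foreseen in the inclusion criteria, so some subjects will fall outside paediatric references. This stands and is built into the recommendation.

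**Conclusion.** The point holds for weight. Testing raw change against zero is a poor choice that the protocol states, not a detail left open. Under the assumed 48-week gains, growth alone gives significance with probability about 0.98 or more at n = 100 and 0.79 or more at n = 50, and a halved gain of 1.25 kg gives the same significant increase with probability 0.98 at n = 100. Gains, SDs and visit-level numbers are assumptions. The qualitative conclusion needs only that mean weight rises with age in most subjects and that visit numbers are not small.

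A reader might extend near-certain significance to blood pressure and pulse. That is not supported at early annual visits, where the probability ranges from below 0.10 to 0.98 depending on drift, SD and n. For these variables the defensible statement is that confounding with age accumulates over years.

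The consequence is p-values that can be mistaken for safety findings. It is not a wrong trial conclusion. The change is worth making because it is cheap and improves the safety read-out.

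**What to change.** In section 10.4.5.3 and the synopsis:

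- Remove the change-from-baseline tests for weight, and for blood pressure and pulse across multi-year follow-up.
- Keep the raw summaries of values and changes with 95% confidence intervals already planned in section 10.3.
- Add mean change in weight-for-age z-score with 95% confidence interval, overall and by corticosteroid use, while subjects are within the age range of a named reference. Use raw values for adults. Weight-for-age is feasible because weight is already scheduled. Table 2 lists height at screening only, so a reference that needs height at each visit is not.
- State beside the table that departure from the reference may reflect corticosteroids or disease as well as ataluren, because there is no control arm.

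The cost is one reference-table derivation and the loss of p-values that have no drug-related interpretation. No new data collection is needed.
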